4.2 Endpoint(s)

Primary Endpoint

- Incidence rate of FVIII inhibitors (≥ 0.6 BU/mL)

Secondary Endpoint(s)

Safety Endpoints:

- Frequency of adverse events (AEs) and serious adverse events (SAEs) reported during the trial period
- Incidence rate of clinically relevant inhibitors defined as an inhibitor titre (≥ 0.6 BU/mL) combined with a decreased recovery (<66% of expected level)
- Incidence rate of high-titre inhibitors defined as inhibitor titre ≥ 5 BU/mL

Efficacy Endpoints:

- Haemostatic effect of N8 on treatment of bleeds assessed on a predefined four point scale: Excellent, Good, Moderate and None
- Annualized bleeding rate
- Number of N8 infusions required per bleed
- Total consumption of N8 per patient (prevention, treatment of bleeds and during surgery) per month and annualised value
- Consumption of N8 (IU/kg/bleed) per bleed
- Consumption of N8 (IU/kg/ months) for bleed prevention

Patient Reported Outcomes (PRO) and Health Economics (HE) End points:

- Change in total scores for parent reported treatment satisfaction
- Health resource utilisation and caregiver burden associated with bleeds

5 Trial Design

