12.1 Definitions

Adverse Event (AE):

Any untoward medical occurrence in a patient or clinical investigation subject administered a pharmaceutical product, and which does not necessarily have a causal relationship with this treatment.

An AE can therefore be any unfavourable and unintended sign (including an abnormal laboratory finding), symptom, or disease temporally associated with the use of a medicinal product, whether or not considered related to the medicinal product.

Note: This includes events from the first trial related activity after the patient has signed the informed consent and until post treatment follow-up period as defined in the protocol.

An AE can also be a clinical laboratory abnormality regarded as clinically significant i.e. an abnormality that suggests a disease and/or organ toxicity, and is of a severity that requires active management (i.e. change of dose, discontinuation of trial product, more frequent follow-up or diagnostic investigation).

A worsening in concomitant illness must be recorded as an AE. A worsening of an ongoing AE should be reported on a new AE form by making a new assessment for seriousness and/or severity.

The following should not be recorded as AEs:

- Pre-planned procedures unless the condition for which the procedure was planned has worsened from the first trial related activity after the patient has signed the informed consent
- Pre-existing conditions found as a result of screening procedures. These should be recorded as medical history/concomitant illness.

Serious Adverse Event (SAE):

A SAE is an experience that at any dose results in any of the following:

- Death
- A life-threatening experience ^{a)}
- In-patient hospitalisation or prolongation of existing hospitalisation ^{b)}
- A persistent or significant disability/incapacity ^{c)}
- A congenital anomaly/birth defect

- Important medical events ^{d)} that may not result in death, be life-threatening ^{a)} or require hospitalisation may be considered a SAE when, based upon appropriate medical judgement, they may jeopardise the patient and may require medical or surgical intervention to prevent one of the outcomes listed in this definition.
 - a) The term “life-threatening” in the definition of SAE refers to an event in which the patient was at risk of death at the time of the event. It does not refer to an event which hypothetically might have caused death if it were more severe.
 - b) The term “hospitalisation” is used when a patient is:

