12.1.2 Medical Event of Special Interest and other events for expedited reporting

A medical event of special interest (MESI) is an event in which, in the evaluation of safety, has special focus.

A MESI should be reported following the same reporting requirements and timelines as for SAEs, irrespective of the MESI fulfils a seriousness criterion.

The following events are defined as MESIs in this trial;

- Medication error
 - Administration of wrong drug
 - wrong route of administration such as intramuscular instead of intravenous
 - Administration of an accidental overdose ie dose which may lead to significant health consequence as judged by the Investigator irrespective of whether a SAE criterion is met.
 - Administration of a high dose with the intention to cause harm
- Inhibitor formation against FVIII
 - blood samples for measurement of FVIII inhibitors will be analysed at the central laboratory selected by Novo Nordisk and if positive (BU $\geq 0.6/\text{mL}$) at two consecutive tests - sampled preferably within 2 weeks - this should be reported by the Investigator as a MESI
- Allergic reaction including Anaphylactic reaction as defined by Sampson et al 2006²⁵. Allergic reactions included but are not limited to any acute immunoglobulin E (IgE) mediated reaction or delayed type hypersensitivity (clinical signs may include various types of skin rashes) that do not meet the definition of anaphylaxis as described by Sampson et al.²⁵
- Thromboembolic events
 - clinical signs or laboratory indications of arterial and venous thrombosis including myocardial infarction, pulmonary embolism, cerebral infarction/thrombosis, deep vein thrombosis, other clinically significant thromboembolic events and peripheral artery occlusion, see definitions)

Other events for expedited reporting;

- Suspected transmission of infectious agents via a trial product.

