The time interval from last N8 dose to start of a bleed will be summarised. This will be done by a frequency tables dividing the time interval into the following 5 groups: ≤ 12 hrs, > 12 hrs and ≤ 24 hrs, > 24 hrs and ≤ 48 hrs, > 48 hrs ≤ 72 hrs, > 72 hrs. The time interval from last N8 dose to start of a bleed will also be illustrated graphically with time from last dose on the x-axis and number of bleedings on the y-axis.

- Number of N8 infusions required per bleed

The number of infusions of N8 required per bleed will be calculated as the number of infusions of N8 used in the time period from start of the bleed to stop of the bleed. The number of infusions will be presented using count and percentages of all bleeds.

- Total consumption of N8 per patient (prevention, treatment of bleeds and during surgery) per month and annualised value

Total consumption of N8 during the trial will be summarised and listed by patient.

- N8 consumption per bleed

The consumption of N8 (IU/kg BW/bleed) will be calculated as the consumption of N8 used from start of the bleed to stop of the bleed. The consumption will be summarised and listed by patient.

- N8 consumption during bleeding prevention period

The consumption of N8 during bleeding prevention period (IU/kg BW/month) will be calculated as the consumption of preventive N8 doses and summarised and listed by patient.

Secondary Safety Endpoints

- Frequency of adverse events and serious adverse events

All AEs and SAEs will be summarised by frequency of events and frequency of patients with any event. Similar summaries cross-classified by severity and by causal relation to trial product will also be made.

Furthermore, listings will be provided displaying all AEs and SAEs including pertinent clinical information.

- Incidence rate of high-titre inhibitors defined as inhibitor titre ≥ 5 Bethesda units/mL

Incidence rate of high-titre inhibitors will be calculated and a 1-sided 97.5% upper confidence limit will be provided based on an exact calculation for a binomial distribution.

- Incidence rate of clinically relevant inhibitors defined as an inhibitor titre (≥ 0.6 BU/mL) combined with a decreased recovery (<66% of expected level)

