Assessments of ~~haematology~~, FVIII trough levels and ~~CD4⁺ T cell count (if applicable)~~ will be done at the local laboratory* as per standard of practice at the participating site. Laboratory results from the local laboratory will be recorded in the eCRF.

~~*in Russia and Hong Kong, CD4+~~

~~T cell count is done centrally~~

2.20 8.2.7.3 Central Laboratory Tests

A central laboratory will coordinate analysis and report of all laboratory safety tests related to biochemistry, viral antibody assessments ~~except CD4⁺ T cell count~~, FVIII inhibitor, FVIII activity and genotyping performed in this trial. Laboratory data from the central laboratory will be reported to Novo Nordisk electronically, and in a manner that anonymity of patients will be maintained.

2.21 8.4.5 Diaries

Diaries will be dispensed and reviewed at all visits, ~~except visits 1, 2 and EoT starting from Visit 2.~~

2.22 12.1.2 Medical Event of Special Interest and other events for expedited reporting

- Inhibitor formation against FVIII
 - *Inhibitor formation is always considered a MESI.* Blood samples for measurements of FVIII inhibitors will be analysed at the central laboratory selected by Novo Nordisk. *However, if an investigator obtains any indication of inhibitor formation by clinical signs or local laboratory results, it should be reported as MESIs.* *The diagnosis of inhibitor is made, if the patient has been tested positive for inhibitors (BU \geq 0.6/mL) at two consecutive tests at the central laboratory, sampled preferably within 2 weeks.* ~~this should be reported by the Investigator as a MESI~~ *However, if the first inhibitor test is positive, it should also be reported as a MESI even though the confirmatory test is negative.*

2.23 23 Responsibilities

The following will be analysed at the local laboratory: ~~haematology~~, FVIII trough level assessment and ~~CD4+ T cell (excluding Russia)~~.

Central and specialized laboratories will analyse and report all laboratory safety tests related to biochemistry, *haematology*, viral antibody assessments, FVIII activity, FVIII inhibitor assessments and potential genotyping performed in this trial. Laboratory data from the central laboratory will be reported to Novo Nordisk electronically. Laboratory data will be reported to Novo Nordisk in a manner that anonymity of patients will be maintained.

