2.39 19.1 Informed Consent Form for Trial Patients	20

2.40	19.4 Regulatory Authorities.....	21
2.41	20 Premature Termination of the Trial/Trial Site	21
2.42	23 Responsibilities	21
2.43	25 Retention of Clinical Trial Documentation.....	22
2.44	Attachment I – Global.....	22

Table of figures

	Page
Figure 12–1	17

Table of tables

	Page
Table 2–1 Visit Flow Chart main trial phase	6
Table 2–2 Visit Flow Chart trial extension phase	6

1 Introduction including rationale for the protocol amendment

The main reasons for this amendment is to re-define the duration and conditions for treatment of patients with inhibitors, restrict the number of previous exposures to blood components (to keep a homogenous PUP population), re-define the trial duration and revise the date of end of trial. In addition, the possibility to further investigate immunogenicity of turoctocog alfa e.g. non-neutralising antibodies assessment and Human Leucocyte Antigen (HLA) genotyping will be introduced. Some changes are administrative to align with updated guidelines and Novo Nordisk Standard Operation Procedures e.g. the requirement to list the participating countries has been removed.

The Patient Information and Informed Consent will be adapted accordingly.

In this protocol amendment:

- Any new text is written ***in italics***.
- Any text deleted from the protocol is written using **strike through**.
- Corrections of minor inconsistencies and ambiguities, and typographical errors will not be listed.

2 Changes

2.1 1 Summary

Trial Design

The trial consists of two phases. In the main phase, an aggregated number of at least 50 patients will receive preventive treatment with turoctocog alfa until they reach a minimum of 50 exposure days² (ED) or until they develop inhibitors. After that the patients will continue in the extension phase ~~until where at least 50 patients should achieve~~ at least 100 ED ~~has been achieved~~, which will translate into a ~~maximum~~ trial duration of up to 3.5 5 years (*including any potential inhibitor treatment*). The estimated total duration of the trial is approximately 5 7 years.

Trial Population

Approximately 60 PUP with severe (FVIII \leq 1%) haemophilia A with no history of inhibitors below 6 years of age ~~in a non-bleeding state~~ will be enrolled to allow for at least 50 patients to complete the trial

Key Inclusion Criteria

- ---

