2.29 11 Concomitant Illnesses and Concomitant Medication

Concomitant medication: any medication, other than the trial product(s), that is taken during the trial, including the screening and run-in periods. Vaccinations must also be recorded as concomitant medication, *and it should include vaccinations performed 1 year prior to Visit 1.*

NB Vaccinations planned ahead of trial participation should be postponed to 3 months after the first turoctocog alfa treatment, as vaccination activates the immune system of the patient, thereby potentially increasing the risk of inhibitor development

2.30 12.1 Definitions

Serious Adverse Event (SAE):

--

- Important medical events^{d)} that may not result in death, be life-threatening^{a)} or require hospitalisation^b may be considered a SAE when, based upon appropriate medical judgement, they may jeopardise the patient and may require medical or surgical intervention to prevent one of the outcomes listed in the definition SAE^d. *Suspicion of transmission of infectious agents via trial product and formation of inhibitory antibodies must always be considered an SAE.*

d) The term “important medical events” means events which may jeopardise the patient or require intervention to prevent a seriousness criterion. It can be AEs which suggest a significant hazard or puts the patient or clinical investigation subject at risk, such as drug interactions, contra-indications or precautions, occurrence of malignancies or development of drug dependency or drug abuse. For example intensive treatment in an emergency room or at home of allergic bronchospasm, blood dyscrasiasis or convulsions that do not result in hospitalisation or development of drug dependency or drug abuse.

Relationship to Trial Product (turoctocog alfa) Assessment Definitions Causality assessment
The following terms are used when assessing the relationship between an AE and the relevant trial product(s):

Probable – Good reasons and sufficient documentation to assume a causal relationship

Possible – A causal relationship is conceivable and cannot be dismissed

Unlikely – The event is most likely related to aetiology other than the trial product.

Outcome Categories and Definitions Final outcome of an AE

- **Recovered/resolved*** – Fully recovered, or by medical or surgical treatment the condition has returned to the level observed at the first trial related activity after the patient signed the informed consent.

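### Inhibitors became automatic SAEs only from Amendment 7, and section 18.2.4 pools SAEs from both periods with no rule for inhibitors diagnosed earlier

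*Combined protocol and SAP*

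**What the plan says.** **Before Amendment 7.** Section 12.1 of protocol version 1.0 does not name inhibitors among SAEs. The criterion most likely to catch them is the one for important medical events, which "may be considered a SAE when, based upon appropriate medical judgement, they may jeopardise the patient". Section 12.1.2 lists inhibitor formation as a MESI, to be reported on the SAE timelines "irrespective of the MESI fulfils a seriousness criterion". Amendment 6 (item 2.22) adds: "Inhibitor formation is always considered a MESI". It gives no automatic SAE status.

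**From Amendment 7.** Item 2.30 adds to the SAE definition that "formation of inhibitory antibodies must always be considered an SAE". The sentence carries the italics that this amendment uses for new text. The last amendment keeps it in section 12.1.

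**The endpoint.** Section 4.2 lists as a secondary safety endpoint "Frequency of adverse events (AEs) and serious adverse events (SAEs) reported during the trial period". Section 18.2.4 gives the analysis: "All AEs and SAEs will be summarised by frequency of events and frequency of patients with any event". The amendment that introduced the two trial phases (item 2.44) reports AEs and SAEs for the main phase and for both phases combined, and adds separate reports for boys who develop inhibitors. No displayed text splits these tables by protocol version or date of diagnosis, or says how inhibitors recorded under the older definition enter them.

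**The concern.** One reported frequency can mix two seriousness rules. Two boys with the same confirmed inhibitor could appear differently in the SAE tables only because one was diagnosed before Amendment 7 and the other after it. The inhibitor is expected in roughly a third of these boys, so its grading could shift the total visibly. A reader of the SAE table could not tell how far a low overall frequency, or a rise over calendar time, reflects the product and how far it reflects the definition in force.

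This is not a complaint that superseded text differs from current text. The current rule is single and clear. The gap is that data collected under both rules enter one summary.

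**Working it through.** The plan states no figure for the SAE frequency, so there is none to reproduce. The check has three parts.

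**1. Could an inhibitor be recorded as non-serious before Amendment 7?** Yes. The MESI wording in version 1.0 makes sense only if some MESIs are not serious, and the important-medical-event criterion rests on judgement. An earlier inhibitor could still be an SAE, through hospitalisation or through that judgement. From Amendment 7 no judgement remains.

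**2. Is there a bridging rule?** None is displayed. Amendment 7 (item 2.33) applies the 24-hour reporting limit to events first recorded as non-serious that later become serious. That is a timeline; it does not tell sites to re-grade inhibitors already recorded.

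**3. How large could the effect be?**

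Inputs from the documents:
- Expected inhibitor rate p = 30–35% (section 12.5.2).
- About 60 boys dosed, for 50 evaluable at 15% drop-out (section 5.3 as amended). Check: 50 / 0.85 = 58.8, so 59, which agrees with about 60.
- Safety Analysis Set = all dosed patients with data after dosing (section 17), so about 60 boys.

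Assumptions, because the documents do not give them:
- f = share of inhibitors diagnosed before Amendment 7.
- g = share of those graded non-serious and not later upgraded.

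Upper bound on the shortfall in the percentage of boys with any SAE = p × f × g.

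| f | g | Shortfall at p = 30% (points) | Shortfall at p = 35% (points) | Boys of 60 |
|---|---|---|---|---|
| 0% | any | 0 | 0 | 0 |
| any | 0% | 0 | 0 | 0 |
| 25% | 50% | 3.75 | 4.4 | 2.25–2.6 |
| 25% | 100% | 7.5 | 8.75 | 4.5–5.25 |
| 40% | 50% | 6.0 | 7.0 | 3.6–4.2 |
| 50% | 50% | 7.5 | 8.75 | 4.5–5.25 |
| 50% | 100% | 15.0 | 17.5 | 9.0–10.5 |

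Example: 0.30 × 0.40 × 0.50 = 0.060 and 0.35 × 0.40 × 0.50 = 0.070. Times 60, that is 3.6 to 4.2 boys.

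These are upper bounds for the patient frequency for two reasons. A boy with another SAE is already counted. And p is applied to every dosed boy: if the 30–35% holds only for the 50 evaluable boys, there are 15–17.5 inhibitors among 60 dosed (25–29%), and the 40%/50% case falls to 5.0–5.8 points (15 × 0.4 × 0.5 / 60 and 17.5 × 0.4 × 0.5 / 60). In the count of events, as opposed to patients, another SAE in the same boy offsets nothing.

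Under one rule for all boys, inhibitors would contribute the full 30–35%, or 18–21 of 60.

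**Length of the older-rule period.** Amendment 7 amends version 4 of 30 November 2012; its own date is not shown. Section 7 plans the first visit for December 2011, about 12 months before version 4. The last amendment, read as replacing 39 by 45, plans 45 months of recruitment ending in Q2 2016. Counting back 45 months from April–June 2016 gives July–September 2012, only 2 to 5 months before version 4. No actual enrolment date is given, so f cannot be derived.

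**The case against.** The strongest case against is that little depends on this table:
- Inhibitor incidence is the primary endpoint, judged on central laboratory tests whatever the AE grading.
- High-titre and clinically relevant inhibitors have their own endpoints.
- Boys with inhibitors get separate AE and SAE reports, and all AEs and SAEs are listed.
- Inhibitors are MESIs in every displayed version, so every case can be found.
- No hypothesis is tested.

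All of this stands. It limits the consequence and lowers the severity, but it does not say how the pooled SAE frequency treats earlier cases.

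A second objection is that the effect may be nil. Diagnoses lag enrolment: the first scheduled inhibitor test after dosing is at 10–15 exposure days, and preventive treatment could at first wait for up to two bleeds. Investigators may have graded most inhibitors serious anyway, since section 3.1 treats them as a most serious complication. MESIs had to be followed to resolution, so one still open at Amendment 7 could have been upgraded. This also stands: zero belongs in the range.

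A reader might infer more than the documents support:
- That the SAE frequency does read low, or that any rise over time is produced by the definition. Each needs at least one earlier inhibitor that was graded non-serious and never upgraded; the documents do not show that one exists.
- That a year or more of recruitment ran under the older rule. That rests on a planned start date, which the plan's own 45-month figure contradicts.
- That the inhibitor incidence itself is distorted. It is not, because it does not use AE seriousness.

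**Conclusion.** The concern holds in a limited form. Section 18.2.4 pools SAEs recorded under two seriousness rules for inhibitors and does not say how those diagnosed before Amendment 7 are counted. The SAE frequency may read low, and may appear to rise over calendar time, if any such inhibitor was recorded as non-serious and left so.

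The size is unknown. It runs from zero to an upper bound set by two shares that the documents do not give; the 40% and 50% behind the 6–7 points are illustrative, not estimates. The conclusion also rests on the displayed text only: not every amendment between numbers 2 and 6 is shown. Severity: minor.

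**What to change.** In section 18.2.4, state that every inhibitor confirmed by two consecutive positive central tests is counted as an SAE in all SAE summaries, whatever protocol version was in force at diagnosis. State also that this is an analysis rule and leaves the investigator's recorded grading unchanged. Show the SAE frequency, by events and by patients, with and without inhibitor events on the Safety Analysis Set.

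Tying the rule to confirmed cases also settles how a single unconfirmed positive, reportable as a MESI since Amendment 6, is treated under it.

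The cost is one sentence and one extra table. No new data are needed, because confirmed cases are identified from the central laboratory results. The reported SAE frequency may become less favourable.

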Table 5–1 Guide for dosing in bleeding episodes¹	11
Table 5–2 Overview of Treatment Regimens	12

1 Introduction including rationale for the protocol amendment

1.1 Overview of changes:

1. Clarified that commercially available FVIII must not be infused prior to enrolment
2. Added withdrawal criteria: Preventive treatment not initiated at age of 24 months
3. Recruitment period has been prolonged
4. Added a new laboratory test: Lupus Anticoagulant
5. Added long term retention of remaining blood samples (Biospecimens)
6. Changed the timing of interim analysis by including inhibitor patients in the “25 patients who need to completed visit 4 before the interim analysis”.
7. Added a new preventive treatment frequency of twice weekly
8. Number of planned sites increased
9. Added monitoring visits every 12 weeks also before patients have been recruited at a site
10. Changed definition of disease related bleedings from being AEs to not being AEs
11. Clarification that the maximum of 2 treatment requiring bleeding episodes, before preventive treatment must start, must be treated with trial product (turoctocog alfa)
12. Clarified dosing for treatment of bleeds
13. Clarified publications of results
14. Clarified dosing guidelines for ITI treatment
15. Clarified timing of CD4+T cells sampling
16. Changed minor inconsistencies, ambiguities and typographical errors

Subject information/Informed consent:

17. Changed minimum mandatory safety text
18. Changed inconsistencies. These changes are considered minor and do not affect the content of the SI/IC and thus will not be listed in this amendment:
 - your treatment changed to your child's treatment
 - investigator changed to trial doctor
 - drug changed to medication
 - doctor changed to trial doctor

1.2 Rational for the changes:

1. The trial product (turoctocog alfa) will be commercially available during the conduct of this trial and must not be used prior to trial enrolment due to that potentially patients that are excluded due to inhibitor developed using turoctocog alfa will bias the primary endpoint
2. It has previously been stated in the protocol that preventive treatment must be initiated before the age of 24 months. This has now been emphasised by adding this to the withdrawal criteria.

3. To ensure possibility of recruiting Chinese patients as the CTA in China has been delayed
4. To align with other PUP trials in haemophilia and to ensure better evaluation of inhibitor patients
5. To ensure a possibility of exploratory analysis in the future on remaining blood samples and to align with other PUP trials in haemophilia
6. To ensure timely interim analysis independent of number of inhibitor patients
7. The gap from once weekly to 3 times weekly infusion of preventive treatment was to big so sites have requested twice weekly frequency to avoid overdosing of patients
8. To ensure the number of planned recruited patients are fulfilled the number of sites are increased
9. 12 weeks between monitoring visits even if there are no patients at site have been reintroduced to ensure a check of trial supplies at site and thus possibility to enrol patients
10. To align with other guardian protocols and Global Safeties current definition of disease related bleedings
11. Ensure no misunderstanding regarding treatment requiring bleeds must be treated with trial product (turoctocog alfa)
12. Sites have requested a guideline for treatment of bleeding episodes
13. Align with current processes for publication of results
14. To guide sites if dosing during ITI treatment
15. Align flow chart with text in protocol
16. Enhance quality of protocol

Subject information/Informed consent:

17. Minimum mandatory safety text has been updated
18. Enhance quality of SI/IC

In this protocol amendment:

- Any new text is written ***in italics***.
- Any text deleted from the protocol is written using **strike through**.

2 Changes

1 Summary

....

Primary Endpoint:

Incidence rate of FVIII inhibitors (≥ 0.6 BU/ml) will be evaluated for the main phase of the trial

Key Secondary Endpoints:

....

Incidence rate of FVIII inhibitors (≥ 0.6 BU)

Key Inclusion Criteria:

....

- No prior use of purified clotting factor FVIII products (previous exposure, equal to or less than 5 ED to blood components, e.g. cryoprecipitate, fresh frozen plasma is accepted) *including commercially available NovoEight®/Novoeight®*

Trial Product

....

~~The dose for treatment of bleeds is decided by the Investigator but should be approximately 25-50 IU/kg in accordance with Guidelines for the Management of Haemophilia[†]. The maximum total daily dose of ruroctocog alfa for the treatment of bleeds is 200 IU/kg with a maximum dose per infusion of 100 IU/kg.~~

2 Flow chart

Table 2-1 Visit Flow Chart main trial phase

Visit number	Screen. Visit 1	Visit 2 [#]	Visit 3	Visit 4	Visit 5	Unscheduled Visit
Visit window	NA	≤ 21 d post V1	10 th - 15 th ED	20 th -25 th ED	50 th -55 th ED	
PATIENT RELATED INFO / ASSESSMENTS						
Consent for genotype test	•,b					
Biospecimen consent	•,b					
FVIII gGenotype test ^f			•b	•b		•b
Lupus Anticoagulant						•b
HE assessment		•	•	•	•	•b
Viral antibody test (if HIV, HBsAg and /or HCV status unknown)	•i, b					•b
T cells subset: CD4+	•b, h	•b, h				•b, h
TRIAL MATERIAL						
Completion session in IV/WRS						
Diary card training		•				

- Visit 2 can be performed at the same day as Visit 1

a – minimum 48 hours washout period of turoctocog alfa (or blood component products at Visit 1)

b – if applicable *or optional*

c – mandatory to confirm clinical relevant inhibitors

d – weight only
 e – Visit 1 trial card only, Visit 2-5 diary card only
 f – if *previous tests are* not available, if allowed by *local* law and after consent
 g – Visit 2 dispensing only
 h – if HIV positive, last value of CD4+ T-cells (if available), or new cell count
 i - if *HIV, HBsAg and/or HCV status unknown*

Table 2-2 presents the rolling visit schedule in the extension phase over the period of one year. It comes to effect after Visit 5 or after ~~ITI~~-inhibitor treatment.

Table 2-2 Visit Flow Chart trial extension phase

Visit type	Dispensing		Assessment & Dispensing	Dispensing		Assessment & Dispensing	End of Trial	Unsc h Visit
Visit number[#]	6	7	8	9	10	11		
Previous visit time(w)	-8	-8	-10	-8	-8	-10	< 8	
Visit window	± 1w	± 1w	± 1w	± 1w	± 1w	± 1w	NA	NA
ASSESSMENTS								
Withdrawal Criteria	●	●	●	●	●	●		●b
Body measurements			●c			●c	●	●a
SAFETY								
Lupus Anticoagulant								●b
FVIII trough level	●a	●a	●a	●a	●a	●a		●a
FVIII recovery	●a	●a	●a	●a	●a	●a		●a
Biochemistry & Haematology			●			●	●	●a
Haematology			●			●	●	●a

OTHER ASSESSMENTS								
HE assessment	•b							
Viral antibody test (if HIV, HBsAg and /or HCV status unknown)							•	•a,b
T cells subset: CD4+							•	•b
TRIAL MATERIAL								
turoctocog alfa administration	•a	•a	•a	•a	•a	•a		•a
Diary card dispensing and/or collection	•	•	•	•	•	•	•d	•b
Review of patient diary and entry of data in eCRF	•	•	•	•	•	•	•	•b,a
Drug dispensing and accountability	•	•	•	•	•	•	•e	•b,a

- Presented numbers are for the first 12 months. Visit numbers for future years will be in consecutive order

a – optional, at discretion of investigator

b – if applicable

c – weight only

d – collection only

e – accountability only

[figure not shown]

Figure 2–1 Trial Design

